4.8.1 Laboratory Data

Descriptive statistics (mean, standard deviation, median, and range) will be calculated for the raw data and for their changes from baseline at each scheduled assessment.

All results will be summarized using shift from baseline. Shifts for clinical laboratory results that can be graded according to CTCAE version 4.0 will be summarized by CTCAE grade.

Summaries by visit will include data from scheduled assessments, and all data will be reported according to the nominal visit date for which it was recorded. Unscheduled data will be included in “worst case post baseline” summaries, which will capture a worst case across all scheduled and unscheduled visits after the first dose of study treatment.

Laboratory data, including urinalysis, will be listed. Pregnancy test results will not be listed, but will be included in datasets.

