5.1.8 End of Treatment Visit

The following procedures will be performed within 30 days (+ 7 days) after treatment discontinuation:

- Serum or urine pregnancy test.
- Physical examination, including neurological examination and including whole-body skin assessment. The examination must include a determination if the patient has had any infection. At the discretion of the investigator, evaluation of any reported infection must be conducted to rule out infection with a microorganism that may be associated with autoimmune or neurological disease(s) as specified in the exclusion criteria.
- Weight and vital signs measurements.
- ECOG performance status.
- Hematology, coagulation panel, and biochemistry parameters.
- Urinalysis and sample collection for assessment of additional renal function studies.
- 12-lead ECG.
- Sample collection for central laboratory assessment of PK, soluble CD25, ADA, and cytokines.
- Sample collection for central laboratory analysis of peripheral WBC populations (Part 2).
- Collection of AE information.
- Collection of concomitant medication information.
- Bone marrow sample (see Section 5.1.7.1).

5.1.9 12-Week Follow-up Visit

Each patient will have a sample taken for assessment of PK and ADA at 12 weeks (± 1 week) after their last dose of ADCT-301.

Blood Sample Collection and Adverse Event Monitoring During Long-Term Follow-up

For all patients, a PK and ADA blood sample collection will be performed 12 weeks (± 1 week) following the last dose of ADCT-301.

For all patients, collection of AEs and SAEs will continue for 84 days (12 weeks) after the last dose of study drug or initiation of new anti-cancer treatment (see [Section 7.3.2.2](#)).

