5.1.10 Long-term Follow-up

Patients who discontinue treatment for any reason other than disease progression will continue to be followed by telephone contact approximately every 12 weeks from the last disease assessment until disease progression or initiation of new anti-cancer treatment. After documentation of disease progression or start of new anti-cancer treatment, patients will be followed (by telephone contact or chart review) approximately every 12 weeks for up to 12 months after the last dose of study drug to collect survival information.

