4.8.2 Adverse Events, Serious Adverse Events, and Deaths

4.8.2.1 Analyses of adverse events

The primary focus of adverse event reporting will be on the TEAEs. A TEAE is defined as an adverse event that occurs or worsens in the period extending from the first dose of study drug to 84 days after the last dose of study drug, or start of new anti-cancer therapy, whichever is earlier.

If an AE date/time of onset (occurrence, worsening, or becoming serious) is incomplete, an imputation algorithm will be used to classify the AE as pre-treatment, TEAE, or post-treatment. For example, if only the day of the AE onset is missing, the year and month will be compared with the first dose and 84 days after the last dose of study drug, or start of new anti-cancer therapy, whichever is earlier. And if the month and day of the AE onset are missing, the year will be compared with the first dose and 84 days after the last dose of study drug, or start of new anti-cancer therapy, whichever is earlier. The algorithm for imputing TEAE will be conservative and will classify an AE as a treatment emergent unless there is definitive information to determine it is non-TEAEs.

Analysis of all TEAE(s):

The following TEAE summaries will be generated for the safety analysis set.

- Overview of TEAEs, summarizing number of TEAEs and number (%) of subjects with any
 - TEAE
 - Related TEAE (including possibly related, probably related, or related)
 - Any \geq grade 3 TEAE
 - Serious TEAE
 - TEAE leading to death

- TEAE leading to permanent treatment discontinuation
- TEAE leading to ADCT-301 delay or reduction or interruption
- TEAE with at least one infusion related reaction
- All TEAEs by PT, showing number (%) of subjects with at least one TEAE, sorted by decreasing incidence of PTs
- All TEAEs by System Organ Class (SOC) and PT, showing number (%) of subjects with at least one TEAE, sorted by SOC in alphabetic order and decreasing incidence of PTs within SOC. This sorting order will be applied to all other AE tables, unless otherwise specified
- All TEAEs by SOC, PT and Maximum CTCAE grade
- All \geq grade 3 TEAEs by SOC, PT and Maximum CTCAE grade
- All related TEAEs by SOC, PT and Maximum CTCAE grade (including possibly related, probably related, or related)
- All Serious TEAEs by SOC and PT by SOC, PT and Maximum CTCAE grade

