4.8.1 Electrocardiogram

ECG parameters (e.g. corrected QT interval [QTcF (Fridericia) or QTcB(Bazett)]) will not be converted or derived, but will be reported as provided by investigational sites.

Descriptive statistics (mean, standard deviation, median and range) for heart rate will be calculated and for their changes from baseline at each scheduled assessment.

The following abnormal QTc (including QTcF, QTcB and QTc with unspecified method) will be reported by a frequency table:

At any post-baseline with absolute value

450 - 480 ms

481 - 500 ms

>= 501 ms

Change from Baseline

31 – 60 ms

>60 ms

For patients with unspecified QTc method at either baseline or post-baseline, consistent correction method is assumed within a patient, when calculating the change from baseline.

All ECG data will be listed, both for quantitative data and for overall interpretation (normal, abnormal –clinically significant, abnormal –not clinically significant) reported by investigational sites.

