6.1.2 Unscheduled visits

Unscheduled visit measurements of laboratory data will be used for computation of baseline and worst values and/or grades. Re-windowing for unscheduled visits will not be performed.

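### The SAP's laboratory worst-case and shift summaries and its QTc table have no end date, while its TEAEs stop at new anti-cancer therapy, so values taken after the next treatment starts can enter them

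*SAP*

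**What the plan says.** **Laboratory tables.** The SAP's Laboratory Data section defines a worst-case post-baseline summary, "which will capture a worst case across all scheduled and unscheduled visits after the first dose of study treatment". It also states: "All results will be summarized using shift from baseline". SAP 6.1.2 adds: "Unscheduled visit measurements of laboratory data will be used for computation of baseline and worst values and/or grades". None of these gives a last date. Protocol 8.6.1.2 states the same open-ended worst-case rule.

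**QTc table.** The Electrocardiogram section counts patients by QTc band "At any post-baseline with absolute value" and by change from baseline, again with no last date. Protocol 8.6.1.3 has a matching open-ended worst-case rule that covers ECGs.

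**Common safety rules.** SAP 4.8 defines baseline but not the end of the observation period. SAP section 4 says that all available data are used.

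**Adverse events.** SAP 4.8.2.1 closes the TEAE period at "84 days after the last dose of study drug, or start of new anti-cancer therapy, whichever is earlier".

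**Collection.** Protocol 5.1.8 places hematology, coagulation, biochemistry and an ECG at the End of Treatment (EOT) visit: "The following procedures will be performed within 30 days (+ 7 days) after treatment discontinuation". After that, protocol 5.1.9 says: "Each patient will have a sample taken for assessment of PK and ADA at 12 weeks". Under protocol 5.1.10, patients who stop for reasons other than progression "will continue to be followed by telephone contact approximately every 12 weeks". Once progression or new treatment is recorded, follow-up is for survival, by telephone or chart review.

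**The concern.** Two parts of the same safety analysis use different observation periods, and the SAP does not explain why. TEAEs exclude what happens after the patient moves to another anti-cancer treatment. The laboratory and QTc tables do not. A programmer who follows the SAP as written would keep any value in the database after first dose, including one drawn after the next treatment began.

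Safety and tolerability is a primary objective, and laboratory tests and ECGs are among the safety endpoints in protocol 8.1. For a worst-case summary the bias has one direction, because an extra value can only leave the worst grade where it is or make it worse. The reader of the report could then see a Grade 4 laboratory value at a dose level with no matching TEAE. Only a search of the listings would show that the value followed another therapy.

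**Working it through.** There is no sample size, power or error rate to reproduce here, since the SAP plans no hypothesis testing. The check has three steps.

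**1. Compare the windows.**

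| Summary | Start | End |
|---|---|---|
| TEAEs (SAP 4.8.2.1) | First dose | Earlier of 84 days after last dose and new anti-cancer therapy |
| Laboratory worst case (SAP Laboratory Data, 6.1.2) | First dose | None stated |
| Laboratory shifts (SAP Laboratory Data) | Baseline | None stated |
| QTc bands (SAP Electrocardiogram) | Post-baseline | None stated |

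**2. Find which values can fall in the gap.**
- Latest scheduled safety laboratory test or ECG: 30 + 7 = 37 days after discontinuation, at the EOT visit.
- The protocol's body text does not require that visit to come before new therapy. The schedule tables in Appendix 13.1 are not reproduced in the copy reviewed, so a timing note there cannot be ruled out.
- The 12-week visit takes PK and ADA samples only, and later contact is by telephone or chart review. Neither schedules a safety laboratory test or ECG.
- Unscheduled laboratory values feed the worst grade without a date limit.

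The exposure is therefore an EOT sample taken after an early start of new therapy, plus any unscheduled values that are entered. By-visit summaries use scheduled assessments only, so only their EOT row is at risk. In that row a late value could move the result in either direction.

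**3. Size the effect.**

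*Per patient, without assuming a frequency.* Tables are by dose level. Protocol 4.1.1 gives cohorts of 3, expanded to 6, and normally no more than 10 patients at a level. One patient whose worst grade changes moves a row by:
- 1/3 = 33 points;
- 1/6 = 17 points;
- 1/10 = 10 points.

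*Across Part 1, on assumptions.* Expected extra patients in a Grade 3-4 row = N × f × (1 − b) × c. N = 50 is the Part 1 maximum in protocol 8.3. The other three inputs are not in the documents and are assumed:
- f, the share with a value after new therapy starts: 0.1 to 0.5;
- b, the share already at Grade 3-4 on that parameter: 0.9, 0.6 or 0.2;
- c, the chance that the new therapy produces Grade 3-4: 0.5 to 0.9.

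| b | Low (f = 0.1, c = 0.5) | High (f = 0.5, c = 0.9) |
|---|---|---|
| 0.9 | 50 × 0.1 × 0.1 × 0.5 = 0.25 patients (0.5 points) | 50 × 0.5 × 0.1 × 0.9 = 2.25 (4.5 points) |
| 0.6 | 50 × 0.1 × 0.4 × 0.5 = 1 (2 points) | 50 × 0.5 × 0.4 × 0.9 = 9 (18 points) |
| 0.2 | 50 × 0.1 × 0.8 × 0.5 = 2 (4 points) | 50 × 0.5 × 0.8 × 0.9 = 18 (36 points) |

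The range is so wide because f, b and c are unknown. It shows what drives the effect and does not estimate it.

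**The case against.** The strongest reply is that the gap is narrow and little depends on it.

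- **Collection limits it.** Scheduled safety laboratory tests and ECGs stop at EOT, and protocol 6.10.1 prohibits other anti-cancer therapy during the study. This stands: the exposure is not an open-ended follow-up period.
- **The SAP follows the protocol.** Protocol 8.6.1.2 and 8.6.1.3 set the same open-ended rule, and the TEAE definition in protocol 8.6.1.1 does not name new therapy. This also stands, so the mismatch lies within the SAP. It explains where the rule came from but does not justify two windows in one report. Protocol 7.3.2.2 itself names the start of new anti-cancer treatment as an end to AE assessment.
- **The tables are descriptive.** They assign no causality, TEAEs are the primary focus, DLTs are observed over one cycle, and the trial ended before escalation was complete. This lowers the stakes, but the laboratory and QTc tables remain part of the safety result.
- **The listings allow a check.** Laboratory and ECG values and subsequent-therapy dates are all listed. This is true, but a reader of the summary table would have to know to look.

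A reader might infer something stronger: that changes caused by the next treatment are in fact counted as ADCT-301 toxicity, that toxicity rates are overstated by a definite amount, or that the laboratory tables contradict the AE tables. The documents do not support this. They show that such values can enter, not that any do. They give no frequency, and two summaries with different windows differ without contradicting each other.

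**Conclusion.** The mismatch is real and visible in the text. The SAP's laboratory worst-case and shift summaries and its QTc table have no end date, while its TEAEs end at new anti-cancer therapy or 84 days after last dose. The rule as written can bias worst grades, and only upward.

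The overall size cannot be derived from the documents and may be small. Blood-count rows would move least if most patients are already at Grade 3-4, which is an assumption; other laboratory parameters and QTc may have more room to move. The firm statement is conditional: if one patient's worst grade changes, a dose-level row of 3 to 10 patients shifts by 33 to 10 points. Combining sparse dose levels, which SAP section 4 allows, would dilute this.

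The conclusion also rests on the unseen Appendix 13.1 tables not requiring the EOT visit to precede new therapy. Even if they did, unscheduled values would remain without a limit. The correction is worth making because it is cheap and removes a one-sided error from a primary safety assessment.

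**What to change.** Add one sentence to the common rules in SAP 4.8: the worst-case and shift laboratory summaries and the QTc frequency table use post-baseline values from first dose to the end of the TEAE window, and later values are listed and flagged only. In by-visit summaries only the EOT row needs attention; values after new therapy can be flagged or excluded there.

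The cost is one sentence and one date filter. The start date of subsequent therapy is already listed under SAP 4.7.2, and the TEAE window already needs it. For scheduled data the new-therapy limit does most of the work, because the last scheduled tests come at EOT. The 84-day limit matters mainly for unscheduled values.

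The downside is that a few late values leave the summaries, possibly including a delayed drug effect. They stay visible in the listings. SAP 3.3 should record the change as a departure from protocol 8.6.1.2 and 8.6.1.3.

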4.8.1 Electrocardiogram

ECG parameters (e.g. corrected QT interval [QTcF (Fridericia) or QTcB(Bazett)]) will not be converted or derived, but will be reported as provided by investigational sites.

Descriptive statistics (mean, standard deviation, median and range) for heart rate will be calculated and for their changes from baseline at each scheduled assessment.

The following abnormal QTc (including QTcF, QTcB and QTc with unspecified method) will be reported by a frequency table:

At any post-baseline with absolute value

450 - 480 ms

481 - 500 ms

>= 501 ms

Change from Baseline

31 – 60 ms

>60 ms

For patients with unspecified QTc method at either baseline or post-baseline, consistent correction method is assumed within a patient, when calculating the change from baseline.

All ECG data will be listed, both for quantitative data and for overall interpretation (normal, abnormal –clinically significant, abnormal –not clinically significant) reported by investigational sites.

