7.3.5 Electrocardiograms

On Day 1 of Cycles 1 and 2, a 12-lead ECG is to be performed before the start of the ADCT-301 infusion, within 30 minutes of the end of infusion, and 3 (± 30 minutes) and 24 (± 2.4) hours after the end of infusion. On Day 1 of Cycle 3 and subsequent cycles, a 12-lead ECG is to be performed before the start of ADCT-301 infusion.

Any abnormalities, including those that worsen from baseline, believed to be clinically significant in the medical and scientific judgment of the Investigator are to be recorded as AEs or SAEs.

Measurement of the QTc interval may be obtained according to the formula used by the institution; however, the Fridericia formula is preferred.¹² The same formula used to confirm eligibility must be applied within a patient for the duration of the study.

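### The SAP's QTc frequency table takes Fridericia, Bazett and unspecified values on common cut-offs with no stated split by method, so for Bazett values a change in heart rate alone can create or hide a count

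*SAP*

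**What the plan says.** SAP 4.8.1 Electrocardiogram introduces the table with "The following abnormal QTc (including QTcF, QTcB and QTc with unspecified method) will be reported by a frequency table". The absolute classes are 450-480, 481-500 and >=501 ms, headed "At any post-baseline with absolute value". The change classes are 31-60 and >60 ms. The same cut-offs serve every correction method. The SAP says that ECG parameters "will not be converted or derived, but will be reported as provided by investigational sites". Where the method is unspecified at baseline or afterwards, "consistent correction method is assumed within a patient, when calculating the change from baseline".

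Protocol 7.3.5 allows the mixture: "Measurement of the QTc interval may be obtained according to the formula used by the institution; however, the Fridericia formula is preferred". It adds: "The same formula used to confirm eligibility must be applied within a patient for the duration of the study".

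Three other provisions matter:

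- Exclusion criterion 18 (protocol 4.2.2) bars a QTc of 450 ms or more at Screening, with pacemaker and bundle branch block exceptions. It names no formula.
- The SAP summarises heart rate separately: "Descriptive statistics (mean, standard deviation, median and range) for heart rate will be calculated".
- Individual data are kept: "All ECG data will be listed, both for quantitative data and for overall interpretation".

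**The concern.** Bazett and Fridericia values agree only at 60 bpm. Above that, Bazett gives the larger number for the same ECG, and the gap widens as heart rate rises. A table with the same cut-offs for both and no method shown therefore mixes two scales.

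The rule of one formula per patient prevents artefacts from switching formula. It does not prevent this one, which arises when both readings are Bazett. The absolute classes count any post-baseline value, so a single ECG at a raised heart rate is enough.

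At stake is how a safety table reads. SAP section 4 lays tables out by dose level, or by merged dose range where few subjects were treated. In small groups, one or two Bazett patients could suggest or blur a dose pattern. From the table alone, a reader could not tell whether a count reflects repolarisation or the site's formula and the patient's heart rate.

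**Working it through.** The plan gives no QTc rate to reproduce. The check uses the definitions of the two named corrections. All QTcF values and heart rates below are assumptions, because the documents give none.

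**Relation.** With RR = 60/HR, QTcB = QT/RR^(1/2) and QTcF = QT/RR^(1/3). Hence QTcB = QTcF x (HR/60)^(1/6).

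**Absolute classes.** At constant QTcF, QTcB reaches a threshold T at HR = 60 x (T/QTcF)^6:

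| QTcF (ms) | 450 ms at | 481 ms at | 501 ms at |
|---|---|---|---|
| 400 | 121.6 bpm | 181.4 | 231.6 |
| 410 | 104.9 | 156.4 | 199.7 |
| 420 | 90.8 | 135.4 | 172.9 |
| 430 | 78.8 | 117.5 | 150.1 |
| 440 | 68.7 | 102.4 | 130.8 |

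The 450 ms column also gives the heart rate at or above which such a patient would fail the entry limit at Screening under Bazett.

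**Relative rise needed.** From a baseline QTcB of b:

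- To reach 450 ms, the heart-rate ratio is (450/b)^6: 1.144 for b = 440, 1.226 for 435, 1.409 for 425 and 1.625 for 415.
- For +31 ms it is (1 + 31/b)^6: 1.493 for b = 449 and 1.565 for b = 400, a rise of about 49-57%.
- For +61 ms it is (1 + 61/b)^6: 2.148 to 2.343 over the same range, a rise of 115-134%.

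The first two are equal when b + 31 = 450, so b = 419. Below about 419 ms, the 31-60 ms change class is reached before 450 ms.

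**Examples at constant QTcF.**

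- QTcF 420, 75 to 95 bpm: 435.9 to 453.4 ms (+17.5). Counted in 450-480 ms.
- QTcF 400, 70 to 110 bpm: 410.4 to 442.5 ms (+32.1). Counted as a 31-60 ms change without reaching 450 ms.
- QTcF 430, 75 to 120 bpm: 446.3 to 482.7 ms (+36.4). Counted in 481-500 ms and as a 31-60 ms change.

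**Opposite direction.**

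- If QTcF rises from 415 to 446 ms (+31) while heart rate falls from 90 to 70 bpm, QTcB goes from 444.0 to 457.6 ms (+13.6), and no change class is entered.
- In the absolute classes, hiding a QTcF above a cut-off requires a heart rate below 60 bpm. QTcF 455 at 50 bpm gives QTcB 441.4 ms.

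**Illustrative frequencies.** Simulated Bazett patients had QTcB <450 ms at baseline, QTcF mean 400-420 ms (SD 15-20) and heart rate mean 75 bpm (SD 10). Each was given the same heart-rate rise at constant QTcF, with values in whole ms:

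| Rise | 450-480 ms | 481-500 ms | Change 31-60 ms |
|---|---|---|---|
| +20 bpm | 13-46% | 0% | 0% |
| +30 bpm | 25-66% | at most 0.1% | 2-5% |
| +40 bpm | 39-76% | 0.4-5% | 52-73% |

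Without rounding, the last change figure is 45-67%. No patient reached >=501 ms or >60 ms, and at most 0.2% had QTcF of 450 ms or more.

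**Opportunities to be counted.** Under protocol 7.3.5 and 5.1.8, a Q3W patient given two cycles has 3 post-dose ECGs in Cycle 1, 4 in Cycle 2 and 1 at End of Treatment: 3 + 4 + 1 = 8. The schedule tables are not shown, so this is not confirmed for weekly dosing.

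**The case against.** The strongest reply is that the SAP made a deliberate choice. Reporting values as supplied is consistent with a protocol that allows institutional formulas, and no document is contradicted. The table is descriptive and no hypothesis is tested. Part 1 is capped at 50 patients, so flagged patients can be checked in the listings. Under protocol 7.3.5, abnormalities judged clinically significant are recorded as adverse events, and those that are treatment-emergent reach the SAP's TEAE tables. Above 60 bpm the absolute classes over-count, which is the cautious direction. All of this stands, and it limits the impact. It does not make the table readable by itself, and the error is not always cautious, because a falling heart rate can conceal a change.

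A second reply is that pooling is inferred from silence. A reader might conclude that the SAP prescribes pooling. It does not say so. It names the three kinds of value and one table, and no table shells are available. Pooling is the natural reading, and one sentence would settle the matter.

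A third reply is that holding QTcF constant treats Fridericia as the heart-rate-free reference. That is an assumption. It follows the protocol's stated preference, but it remains an assumption.

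**Conclusion.** The point holds as a low-severity, cheap improvement. As written, the table cannot separate a QTc change from the combination of site formula and heart rate. The class most easily affected is 450-480 ms. The 31-60 ms change class is affected about as often for rises near 40 bpm, and is reached first from a baseline QTcB below about 419 ms. The 481-500 ms class is reached less often, and >=501 ms and >60 ms only at extreme rates.

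A reader might infer that this trial's QTc counts are inflated. The documents do not support that. They give neither the share of Bazett ECGs nor the heart rates, so the effect runs from nil (all Fridericia) to material (mostly Bazett with raised heart rates). Nor is a dose decision shown to be at risk: dose-limiting toxicities and the maximum tolerated dose are not defined from this table.

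**What to change.** In SAP 4.8.1 Electrocardiogram, keep the cut-offs and the as-reported listing, and make four changes.

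1. Show the absolute and change categories in separate rows for QTcF, QTcB and unspecified, each with its own n.
2. Where a patient's method is labelled at one time point and unspecified at another, apply the SAP's consistent-method assumption and treat both as the labelled method. Keep values with no method at any time point in the unspecified row.
3. Add one supplementary QTcF-scale count covering both the absolute and the change categories. Use reported QTcF, plus QTcB x (60/HR)^(1/6) where the same ECG has a heart rate, rounded to whole ms. State the denominator: patients with at least one QTcF-scale post-baseline value, and also a QTcF-scale baseline for the change categories.
4. Amend the sentence that rules out conversion so that it allows this one derivation.

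The cost is a few table rows and one formula using the ECG heart rate that the SAP already summarises. Rounding adds about +/-1 ms: a recorded 460 ms at 100 bpm converts to 422.5 ms, with a range of 421.6-423.3 when the inputs vary by 0.5 ms and 0.5 bpm. Counts per row become smaller, and fully unspecified values stay unconverted, so the supplementary count may cover fewer patients than the as-reported rows together.
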